2.2.1.5 Sensitivity Analysis: The Second (Born) Twin

The second twin is the one who is assigned to the same treatment group as the first (born) randomized twin.

The following analyses will be performed on FAS to include the second twin.

One analysis will repeat test the primary and key secondary endpoints replacing the first-randomized twin by the second twin.

Another analysis will be a hierarchical mixed model that includes both twins in a way that accounts for the possible correlation between them. For the mixed effects model, the dependent variable will be the number of days, the independent variable is the treatment group, with gestation age group and the region (North America, Europe, and Israel) as two class covariates. A twin effect will be included in the model as a random cluster effect. For each singleton, the cluster has one subject, and for each twin the cluster will have two subjects. This random cluster effect is used to model the correlation within each twin-pair under the compound symmetry covariance structure.

Confidential Page 26 of 40

Statistical Analysis Plan V1.3 SAP Date: 06APR2018

For infants who experience NEC (Necrotizing Enterocolitis) or death, their ranks will be assigned in the same way as described in Section 2.2.1.3.2.

2.2.1.6 Sensitivity Analysis: The Per Protocol Set

Per protocol set consists of subjects in FAS who do not have any important protocol deviations. The important protocol deviations will be determined before the database is unblinded. The analysis of the primary and the key secondary endpoint will be repeated on the per protocol set.

2.2.1.7 Sensitivity Analysis: Breaking Tied NFE Rankings

For the infants who have the same NFE value which lead to the tied NFE rankings, their baseline enteral feeding volume will be used to break the tie. Specifically, the infant with the lowest baseline enteral feeding volume will be ranked lowest among them, the infant with the second lowest enteral feeding volume will be ranked the second lowest, and so on. For infants who have the same NFE rank and the same baseline enteral feeding volume, their NFE ranks will remain to be tied. For subjects who have unique NFE rankings, they will retain their ranks if there were no ties. For infants who experience NEC (Necrotizing Enterocolitis) and infants who die, their NFE will be assigned to Day 29 and Day 30 without breaking ties by their baseline enteral feeding volume. The individual ranks among subjects experiencing NEC and the individual ranks among subjects who die will be handled according to Section 1.3.3. For subjects who didn't meet the enteral feeding criterion during the treatment period, their NFE will be censored on Day 28 without breaking by their baseline enteral feeding volume. The testing of such NFE ranking will be analyzed in the same way as described in 2.2.1.1 for the van Elteren test, stratified by gestational age group and region (North America, Europe, and Israel).

2.2.1.8 Supportive Analysis: Infants Who Achieved Partial Enteral Feeding

The number and percent of infants who achieve enteral feeding of at least 150 ml/kg/day for at least 3 consecutive days, only two consecutive days, and just one day will be summarized for each treatment group.

2.2.2 Other Secondary Endpoints

The following other secondary endpoints will be analyzed on FAS only.

- Growth velocity (g/kg/day) at 6, 8, and 10 days, the last day of treatment (or Day 28), day of discharge, 3-month follow-up, 12-month follow-up, and 24-month follow up
- Change in Z-score at 6, 8 and 10 days, the last day of treatment (or Day 28), day of discharge, 3-month follow-up, 12-month follow-up, and 24-month follow up from initiation of treatment
- Gain in body weight at 6, 8, and 10 days, the last day of treatment (or Day 28), day of discharge, 3-month follow-up, 12-month follow-up, and 24-month follow up

Confidential Page 27 of 40

• Number and percentage of infants reaching full enteral feeding within 6, 8, and 10 days from initiation of treatment.

- Total number of days receiving parenteral nutrition
- Number of days to 120Kcal/kg/day
- Number of days to wean-off PN

For the continuous variables (growth velocity, z-score, body weight), ANCOVA analysis will be performed at each time point of interest, including treatment, the stratification factors of gestation age and region (North America, Europe, and Israel) as class variables, and the baseline values as a continuous covariate, the estimated treatment differences (NTRA-2112 minus placebo), 95% confidence intervals, and P-values will be provided.

For the variable of number of day to a given event, the van Elteren test stratified for gestation age and region will be performed. The average score will be used for the ties. Infants who experience NEC (Necrotizing Enterocolitis) and infants who die will be assigned the second worst and the worst ranks. The individual ranks among subjects experiencing NEC and the individual ranks among subjects who die will be handled according to Section 1.3.3.

For percent of infants reaching full external feeding, Cochran-Mantel-Haenszel (CMH) test stratified for gestation age and region will be performed.

Statistical testing of these other secondary endpoints will be considered exploratory and will not control for Type I error rate inflation.

No imputation will be performed for the missing values for the other secondary endpoints.

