1.3.3 Sample Size and Statistical Power Considerations

Presentation of sample size is based on the hypothesis that NFE in either treatment group is shorter than in the placebo group. Based on limited historical data (Phase 2), the

Confidential Page 14 of 40

conservative mean is 8.0 days for the placebo group and 6.6 days for each of the 2 active dose groups. This assumes a standard deviation of 3.5 days for each group.

The analysis will be based on a nonparametric test. The NFEs for each infant in the FAS will be ranked from shortest time (the best outcome) to longest time. Infants who do not achieve full enteral feeding and also experience necrotizing enterocolitis (NEC) will be assigned the next set of ranks; all the infants experiencing NEC will be ranked in terms of their time to NEC (the earlier the worse) and will be assigned ranks one greater than the rank of the longest time to achieve NFEs. All infants who do not achieve full enteral feeding and die will be assigned the next set of ranks, again with the earliest deaths assigned the largest (i.e. worst) rank. Thus, each infant who has achieved EN or who has died or suffered NEC will have a recorded rank.

Randomization will be stratified by center and by gestational age group. The statistical analysis will stratify the infants by gestational age group and region (North America, Europe, and Israel), but not by center. Because the analysis will be based on ranks, a van Elteren test will be used to compare NTRA-2112 to placebo. To calculate sample size, an independent groups t-test for 85% power to account for the reduced power of the non-parametric test was used (i.e., expect that a t-test with 85% power to have at least 80% power when the van Elteren test is applied). A two-side 5% test will be used to compare each active dose to placebo. These calculations give N = 115 infants per group. To account for the reduction in power caused by potential missing data, the sample size was increased to 130 per group or a total sample size of 390

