1.6.5 Missing Data Handling Rules

The primary approach to handling missing ranks for the primary and the key secondary endpoints will be multiple imputation. The details are provided in Section 2.2.1.3.

No imputation will be made for other secondary or exploratory endpoints. No imputation will be made for any safety or lab measurements.

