2.2.1.4 Sensitivity Analysis: Missing Values

Some infants in the FAS are expected to drop out of the study or, for some other reason, not to have a ranking. As described in Section 2.2.1.3, multiple imputation will be used to include these infants in the analysis of the primary and key secondary endpoint.

The following sensitivity analyses will be conducted on the primary and key secondary endpoint to explore the effect of these missing values:

- Worst reasonable case analysis: Infants in an NTRA-2112 group with a missing rank will be assigned the median rank in the placebo group and infants in the placebo group with a missing rank will be assigned the median rank in the combined NTRA-2112 groups. The van Elteren test, stratified by gestation age group and region (North America, Europe, and Israel) will be performed.
- **Best reasonable case analysis**: Infants in an NTRA-2112 group with a missing rank will be assigned the median rank in the respective NTRA-2112 group and infants in the placebo group with a missing rank will be assigned the median rank in the

Confidential Page 25 of 40

placebo group. The van Elteren test, stratified by gestation age group and region (North America, Europe, and Israel) will be performed.

Tipping point analysis: Infants in either of the NTRA-2112 groups with a missing rank will be assigned varying ranks to find the point at which statistical significance is lost. Specifically, if the outcome of the hypothesis test is in favor of a NTRA-2112 group over the placebo group (P-value <0.05), then one day will be added to each of the imputed values for the NTRA-2112 group in each copy of the imputed dataset, whilst the data for the placebo group will remain the same. The 5 imputed datasets will then be combined to run the van Elteren test results using PROC MI procedure in SAS. This "day shifting" will be repeated with one extra day at a time until the outcome of the hypothesis test is no longer in favor of the NTRA-2112 group over the placebo group (i.e. the P-value becomes greater than 0.05). As the overall ranks of NTRA-2112 group increase as the results of adding one day each time to each imputed missing rank, the highest rank for the imputed missing ranks will be truncated at Day 30 (implying that a missing data point is as bad as a death).

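### SAP 2.2.2 gives no rank to infants who are alive, NEC-free and never reach 120 kcal/kg/day or wean off PN, so by default they leave the van Elteren test

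*SAP*

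**What the plan says.** SAP 2.2.2 sets the test: "For the variable of number of day to a given event, the van Elteren test stratified for gestation age and region will be performed". Two listed endpoints are clearly of this kind: days to 120 kcal/kg/day and days to wean off PN. The same section then says "Infants who experience NEC (Necrotizing Enterocolitis) and infants who die will be assigned the second worst and the worst ranks" and refers to SAP 1.3.3 for the order within those two groups. It closes the matter of missing data with "No imputation will be performed for the missing values for the other secondary endpoints". SAP 1.6.5 repeats this: "No imputation will be made for other secondary or exploratory endpoints".

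The primary and key secondary endpoints are treated differently. SAP 1.6.5 says: "The primary approach to handling missing ranks for the primary and the key secondary endpoints will be multiple imputation".

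SAP 1.3.3, written for the primary endpoint, summarises who is ranked: "Thus, each infant who has achieved EN or who has died or suffered NEC will have a recorded rank". The only visible rule for an infant who is alive, NEC-free and has not succeeded is in SAP 2.2.1.7: "For subjects who didn't meet the enteral feeding criterion during the treatment period, their NFE will be censored on Day 28". It belongs to one sensitivity analysis of NFE.

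Protocol 12.4.7 left it to the SAP to set out the missing-data approach for these other secondary endpoints.

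**The concern.** A rank test needs a value or a rank for every infant it analyses. An infant still on PN when observation ends is not missing in the ordinary sense: the infant was watched and did not reach the event. SAP 2.2.2 does not separate that observed failure from a record cut short by withdrawal. With no rank assigned and imputation barred, standard software leaves both out.

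The comparison would then be among infants who reached the event, plus NEC and deaths. Membership of that group is decided after randomisation and may depend on treatment. If one arm has more infants who never wean, that difference does not enter the test. This can hide a benefit (fewer failures on active) or a disadvantage (more failures on active, with faster times among those who succeed). Because the rule is open, a programmer would also have to choose one, possibly after seeing the data.

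**Working it through.** **Text check: who has a rank under 2.2.2?**

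| Infant's status at the end of observation | Rank under SAP 2.2.2 |
|---|---|
| Reached the event | Observed day |
| NEC | Second worst |
| Died | Worst |
| Follow-up stopped early, no event | None; imputation barred |
| Alive, NEC-free, observed to the end, no event | None stated; imputation barred if this counts as missing |

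The last row is the gap. The SAP does expect unranked infants beyond drop-outs. For the primary and key secondary endpoints, SAP 2.2.1.4 says: "Some infants in the FAS are expected to drop out of the study or, for some other reason, not to have a ranking". There, multiple imputation takes them up; here nothing does.

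**Size: inputs.** The plan states no figure for this point, so there is none to reproduce.
- n = 130 per arm (SAP 1.3.3).
- Mean days 8.0 placebo and 6.6 active, SD 3.5 (SAP 1.3.3). These are NFE figures, borrowed because none are given for the two endpoints.
- Non-attainment, p_A (active) and p_P (placebo): not in the documents. Assumed, from near zero to 20%.
- Two-sided 5% test.

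**Approximation, equal speed among achievers.** Let θ be the chance that a random active infant does better than a random placebo infant, counting ties as half.
- Non-attainers dropped: θ = 0.5, so benefit is declared in about 2.5% of trials whatever p_A and p_P are.
- Non-attainers ranked tied behind all achievers: θ = ½(1−p_A)(1−p_P) + (1−p_A)p_P + ½p_A·p_P = ½ + (p_P − p_A)/2.
- Standard error of the Wilcoxon estimate, ignoring ties: √[(2n+1)/(12n²)] = √[261/(12 × 16,900)] = 0.0359.
- p_A = 5%, p_P = 15%: θ = 0.55; z = 0.05/0.0359 = 1.39; power = Φ(1.39 − 1.96) = Φ(−0.57), about 29%.
- p_A = 2%, p_P = 5%: θ = 0.515; z = 0.015/0.0359 = 0.42; power = Φ(0.42 − 1.96) = Φ(−1.54), about 6%.

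**Simulation.** Two-stratum van Elteren test, lognormal days, 4,000 runs per row (10,000 for the 2% versus 5% row), NEC and deaths left out.

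| Non-attainment, active / placebo | Mean days among achievers, active / placebo | Result counted | Dropped | Ranked as failures |
|---|---|---|---|---|
| 10% / 10% | 8.0 / 8.0 | either direction | 5% | 5% |
| 2% / 5% | 8.0 / 8.0 | favours active | 2.5% | 6% |
| 5% / 15% | 8.0 / 8.0 | favours active | 3% | 29% |
| 15% / 5% | 8.0 / 8.0 | favours placebo | 3% | 30% |
| 20% / 5% | 8.0 / 8.0 | favours placebo | 2.5% | 57% |
| 15% / 5% | 6.6 / 8.0 | favours active | 95% | 39% |
| 5% / 15% | 6.6 / 8.0 | favours active | 96% | 99% |

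Another set of runs at 2% versus 5% gave about 7% when ranked, so 6 to 7% is a fair statement.

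**How common could non-attainment be?** If the NFE inputs carried over, the chance of exceeding Day 28 would be tiny. Normal: (28 − 8)/3.5 = 5.7 SD, effectively zero. Lognormal: σ² = ln[1 + (3.5/8)²] = 0.175, σ = 0.418, μ = ln 8 − 0.175/2 = 1.992; z = (3.332 − 1.992)/0.418 = 3.2, about 0.07%. At that level the choice of rule has no visible effect.

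**The case against.** A reader might infer that the SAP orders non-achievers to be dropped. It does not. SAP 2.2.2 specifies the FAS, and the bar on imputation concerns missing values, whereas an infant seen to be still on PN has a known status. SAP 3.1 ties missing values to drop-out and early termination. SAP 2.2.1.7 censors NFE non-achievers on Day 28, and SAP 2.2.1.3.2 puts NEC at 29 days and death at 30, so a programmer could carry that convention over and arrive close to the fix below. This stands: exclusion is the default result of an incomplete rule, not a stated instruction. But the convention is written for NFE only, and nothing extends it to 2.2.2.

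A reader might also infer that failures in general leave the comparison. They do not. NEC and deaths keep the worst ranks, the proportions reaching full feeding by days 6, 8 and 10 have their own CMH test, and total PN days needs no wean-off event. Nor is an inflated false-positive rate shown: with equal failure rates and equal speed, both analyses hold about 5%. What is shown is masking of a difference in failures.

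The size can fairly be disputed. Inclusion criterion 8 expects each infant to wean at the primary hospital, and SAP 2.1.10 summarises PN to discharge, so few may remain unweaned. When active is faster and also fails less, dropping costs little (96% versus 99%). Against this, the NFE inputs come from a Phase II population of at least 750 g (Protocol 5.1), while this trial admits 500 g. SAP 3.1 considers SDs of 4 and 5 days. SAP 2.1.12 lists transfer to another hospital, which may end observation before weaning.

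Section 2.2.1.3.1 is not readable in the available text and is not held against the plan. SAP 1.6.5 and 3.1 connect it to the primary and key secondary endpoints.

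**Conclusion.** The point holds for two endpoints: days to 120 kcal/kg/day and days to wean off PN. SAP 2.2.2 leaves infants who are observed to the end, alive and NEC-free, without the event and without a rank, and its default consequence is that they leave the test. The direction of the problem is secure: dropping them removes any difference in failure rates, whichever arm it favours. The size is not secure, because it rests on assumed non-attainment rates and on time inputs borrowed from NFE. It ranges from negligible near zero non-attainment to a large change in the result at 15% versus 5%.

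Severity is minor. SAP 2.2.2 calls these tests exploratory without type I error control, and they lie outside the hierarchy in SAP 1.7. No confirmatory conclusion depends on them.

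**What to change.** In SAP 2.2.2, for each of the two endpoints:

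1. State the observation window: when it closes, and whether discharge or transfer closes it.
2. Give infants observed to that close, alive, NEC-free and without the event, one shared tied rank behind every achiever and ahead of every NEC case and death.
3. Treat as missing, and leave unimputed, only infants whose follow-up stopped before the window closed.

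The cost is about one sentence in the SAP and one coding rule, with no new data collection. It should be in place before the unblinding described in SAP section 2. Infants lost early would still be left out, so the counts in each category should be shown by arm.

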2.2.3 Exploratory Secondary Efficacy Endpoints

The FAS will be used to analyze the exploratory secondary efficacy endpoints. The continuous variables will be analyzed using ANCOVA analysis at each time point of interest, including treatment, the stratification factors of gestation age group and region (North America, Europe, and Israel) as class variables, and the baseline values as a continuous covariate, the estimated treatment differences (NTRA-2112 minus placebo), 95% confidence intervals, and P-values will be provided.

For percent enteral feeding from total nutrition and percent parenteral nutrition from total nutrition, CMH test stratified for gestation age group and region (North America, Europe, and Israel) will be performed.

- Number of days to end gastric residuals over 2 ml
- Gain in length at 6, 8 and 10 days, the last day of treatment (or Day 28), day of discharge, 3-month follow-up, 12-month follow-up, and 24-month follow up from initiation of treatment

Confidential Page 28 of 40

- Gain in head circumference during the treatment period and follow up period (long term follow-up period)
- Percent enteral feedings from total nutrition
- Percent parenteral nutrition from total nutrition

Graphical presentation of the average weight, height, and head circumference over time by treatment group will be provided.

2.2.4 Analysis of Predictor Variables

The effect of the following predictor variables on the primary and key secondary endpoints will be assessed by calculating descriptive statistics of the primary and key secondary endpoints in each category of predictor class variables on FAS.

- Gestation age group
- Region (North America, Europe, and Israel)
- Birth weight (< 750g, $\ge 750g$ and < 1000g, $\ge 1000g$ and < 1500g, $\ge 1500g$)
- Gender
- Ethnicity
- Enteral feedings type:
 - o Only own mother's milk
 - Only donor breast milk
 - o Only human milk (combined)
 - o Only Infant formula
 - Only own mother's milk and formula, in any combination of proportions
 - Only donor breast milk and formula, in any combination of proportions
 - Only human milk and infant formula, in any combination of proportions

2.3 SAFETY ANALYSIS

All safety analyses will be performed on the Safety Analysis Set. Safety data presented by treatment group will be summarized on an "as treated" basis. Safety variables include the extent of exposure, treatment-emergent adverse events (TEAEs), clinical laboratory parameters, vital signs, and other relevant variables. Study Day 1 for all safety analyses is defined as the date of the first dose of study drug.

Both fraternal and identical twins enrolled in the study, will be included in the safety analyses.

2.3.1 Treatment Compliance

The compliance check will be based on the ratio of number of enteral feeds with study drug administered over the total number of feeds planned for the subject's treatment

Confidential Page 29 of 40

duration (days). The following describes the calculation algorithm for individual subject compliance based on the information on eCRF.

- 1. If no study drug was missed for the day, then the daily compliance is 100%.
- 2. If the study drug was missed for the day, then based on how many feeds were missed and how many feeds were planned for the day, the daily compliance will be calculated as the ratio of number of feeds with study drug administered over the number of feeds planned x 100%.

For each subject, the daily treatment compliance will be calculated for each day while the subject was supposed to receive the treatment.

For an infant, the average of the daily compliance over the treatment period (up to Day 28) will be the overall treatment compliance for this infant.

The overall treatment compliance values will be summarized using descriptive statistics for each treatment group.

A subject data listing of treatment compliance will be provided.

2.3.2 Safety Outcome Variables

The following safety data will be collected: reported AEs (including SAEs), clinical chemistry, physical examination, vital signs, respiration status, complete blood count, glucose level, anti-insulin antibodies, and stool frequency and consistency.

All safety measurements will use all available data for analyses, including data from unscheduled visits and repeated measurements.

Change from baseline to each post-treatment time point where scheduled assessments were made will be calculated for relevant measurements.

No safety data will be imputed. The handling of partial/missing dates for AEs and prior/concomitant medications is detailed in Appendix 6.1.

2.3.2.1 Adverse Events

Adverse events (AEs) experienced by the subjects will be collected from initiation of dosing through the final study visit and will be coded using the latest version of the Medical Dictionary for Regulatory Activities (MedDRA) per the Data Management Plan.

Adverse event data will be categorized according to their onset date into the following study periods:

• Treatment-emergent adverse events are the ones that they started during or after administration of the first dose of study medication up till the last dose date + 30 days. In addition, medical history events that worsen in severity after the start of dosing will be considered treatment-emergent adverse events.

Confidential Page 30 of 40

AEs during the 3 month corrected age follow up period : < last dose date + 30 days -
 Month 3 follow-up visit

- AEs during the 12 month corrected age follow up period : < Month 3 follow-up visit <= Month 12 follow-up visit
- AEs during the 24 month corrected age follow up period : < Month 12 follow-up visit <= Month 24 follow-up visit

If an AE has a missing onset date then unless the stop date of the AE indicates otherwise, this will be considered an ongoing AE. Similarly, if an AE has a partial onset date, then unless the partial onset date or the stop date indicates otherwise, this will be considered an ongoing AE.

Only those AEs that are treatment-emergent will be included in summary tables. All AEs, treatment-emergent or otherwise, will be presented in subject data listings.

TEAEs will be summarized by treatment group, separately for the four reporting periods above. The incidence of TEAEs will be reported as the number (percent) of subjects with TEAEs within SOC and PT. Subjects will be counted only once within a SOC and PT, even if the subject experienced more than one TEAE within a specific SOC and PT. The number (percent) of subjects with TEAEs will also be summarized by maximum severity of Common Terminology Criteria for Adverse Events (CTCAE) and the relationship to the study drug (unlikely, possible, probable).

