11.3. Collecting, Recording and Reporting of Adverse Events and Serious Adverse Events

Treatment-emergent AEs are events that are not present at screening, or if present at screening, have worsened in severity or frequency.

Data regarding all treatment-emergent AEs will be collected in this study and recorded in the source documentation and in the eCRF, whether or not the event is attributed to trial medication. Pre-treatment emergent events will not be considered as AE and will be recorded as medical history.

Adverse event monitoring will be captured throughout the study from Day 1 (initiation of dosing) until the final study visit (follow-up visit).

AEs and SAEs will be evaluated daily during the treatment period. An additional safety evaluation will be performed at discharge or end of treatment and at final study visit (follow-up visit).

The following information will be recorded: description, date of onset and end date, severity, assessment of relatedness to trial medication, other suspect drug or device, and action taken. Follow-up information should be provided as necessary. The investigator will assess AEs for severity, for relationship to the study drug, and as to whether the event meets one or more of the definitions of an SAE.

AEs will be graded on a 5-point scale (mild, moderate, severe, life-threatening, and death) and reported as indicated in the source documentation and in the eCRF. Severity of such an AE is defined as follows:

Table 2: Severity Assessment Terminology for Reporting Adverse Events

CTCAE Grade	Common Term	Description	
1	Mild	Mild; asymptomatic or mild symptoms; clinical or diagnost observations only; intervention not indicated.	
2	Moderate	Moderate; minimal, local or noninvasive intervention indicated; limiting age-appropriate instrumental Activities of Daily Living (ADL).	
3	Severe	Severe or medically significant but not immediately lifethreatening; hospitalization or prolongation of hospitalization indicated;	
4	Life-threatening	Life-threatening consequences; urgent intervention indicated.	

5	Death	Outcome of AE was death
---	-------	-------------------------

AEs that are not described on the CTCAE v 4.03 will be graded using the scale in Table 2.

In order to classify adverse events and diseases, the sponsor or designee will use the Medical Dictionary for Regulatory Activities (MedDRA) to assign preferred terms to the original terms entered in the eCRF.

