12.2.4. Safety

Serious adverse events and adverse events occurring at any time during the trial or follow-up will be listed and summarized.

The incidence of (1) NEC and (2) death will be compared between the treatment groups.

Safety assessments will include:

- Length of exposure to study medication
- Physical examination and vital signs
- Blood chemistry and haematology

⁷ For example, one of a twin pair may remain in the hospital despite readiness for discharge until his/her sibling is also ready for discharge, so that both can be discharged at the same time.

Concomitant medications

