2.3.2.2 Deaths, Serious and Other Significant Adverse Events

The number (percent) of subjects with TEAEs leading to death will be summarized by MedDRA SOC and PT for each treatment group separately for the on-study period and the long-term follow-up period. A subject data listing of all AEs leading to death will be provided.

The number (percent) of subjects with treatment-emergent serious adverse events (SAEs) will be summarized by MedDRA SOC and PT for each treatment group, separately for the on-study period and the long-term follow-up period. A subject data listing of all SAEs will be provided.

The number (percent) of subjects with TEAEs leading to discontinuation from study treatment will be summarized by MedDRA SOC and PT for each treatment group during the on-study period. A subject data listing of all AEs leading to discontinuation from study treatment will be provided.

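### The SAP closes the treatment-emergent window 30 days after last dose and tabulates only treatment-emergent events, yet promises such tables for follow-up periods that start after the window

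*SAP*

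**What the plan says.** SAP 2.3.2.1 sorts adverse events by onset date into four periods. The first is the treatment-emergent period, for events that "started during or after administration of the first dose of study medication up till the last dose date + 30 days". Medical-history conditions that worsen in severity once dosing has begun also count, with no end date given. The other three periods run to the 3-, 12- and 24-month corrected-age visits.

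Two instructions follow. One is "Only those AEs that are treatment-emergent will be included in summary tables", with all other events going to listings. The other is "TEAEs will be summarized by treatment group, separately for the four reporting periods above".

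SAP 2.3.2.2 states: "The number (percent) of subjects with TEAEs leading to death will be summarized by MedDRA SOC and PT for each treatment group", split into an on-study and a long-term follow-up period. The SAE table has the same restriction and the same split. Neither period is defined there or tied to the four periods of 2.3.2.1.

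Protocol 11.3 sets no end date: "Treatment-emergent AEs are events that are not present at screening, or if present at screening, have worsened in severity or frequency". It has adverse events collected from first dose to the final study visit. Protocol 12.2.4 adds "Serious adverse events and adverse events occurring at any time during the trial or follow-up will be listed and summarized" and "The incidence of (1) NEC and (2) death will be compared between the treatment groups".

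SAP section 4 reports only that the AE reporting periods were defined further. It does not declare a window narrower than the protocol's.

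**The concern.** By the SAP's own definition, a new event in any of the last three periods cannot be treatment-emergent. The table programmer therefore has to break one of the two instructions in 2.3.2.1, and the SAP does not say which.

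- **If the restriction governs,** late new-onset AEs, SAEs and fatal events leave the by-arm tables. By-arm counts of NEC and death over the whole of follow-up would have to be assembled from listings.
- **If the four-period promise governs,** late events are tabulated as treatment-emergent although they fail the definition.

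SAP section 2 sets data cleaning, unblinding and the primary analysis at the last infant's 3-month corrected-age visit, so the ambiguity affects the main report as well as the later follow-up.

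**Working it through.** **Comparison of the rules**

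| Question | Protocol | SAP |
|---|---|---|
| When does treatment-emergent end for a new event? | No end (11.3) | Last dose + 30 days (2.3.2.1) |
| What counts as worsening? | Severity or frequency (11.3) | Severity only (2.3.2.1) |
| Which AEs are summarised? | Any time in trial or follow-up (12.2.4) | Treatment-emergent only, yet in four periods (2.3.2.1) |
| Which SAEs and fatal events are summarised? | Any time (12.2.4) | Treatment-emergent only, yet also in long-term follow-up (2.3.2.2) |
| Are NEC and death compared by arm? | Yes (12.2.4) | No such comparison in the supplied text of 2.3, although 1.2.4 names both among the safety endpoints |

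Under the literal SAP rule, the follow-up AE tables would hold only worsened medical-history conditions. The follow-up death table might also hold late deaths from events that began inside the window.

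**How much time lies outside the window**

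The plan gives no figure to reproduce. The inputs are:

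- at most 28 treatment days (Protocol synopsis)
- treatment start by day 5 of life (SAP 1.3.2), taken here as day 1 to day 5
- gestation 26 to 32 weeks (Protocol 8.2)
- 40 weeks as term for corrected age (Protocol section 3)
- assumed: full 28-day dosing, 3 months = 13 weeks = 91 days, 24 months = 730.5 days

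Window end = 28 + 30 = study Day 58. In days of life this is start day + 57, so 58 (start on day 1) to 62 (start on day 5).

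Days from birth to a corrected-age visit = (40 − gestational weeks) × 7 + corrected age in days.

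| Gestation | Visit | Days from birth | Outside, start day 1 | Outside, start day 5 |
|---|---|---|---|---|
| 26 wk | 3 months | 98 + 91 = 189 | (189 − 58)/189 = 69.3% | (189 − 62)/189 = 67.2% |
| 32 wk | 3 months | 56 + 91 = 147 | (147 − 58)/147 = 60.5% | (147 − 62)/147 = 57.8% |
| 26 wk | 24 months | 98 + 730.5 = 828.5 | 770.5/828.5 = 93.0% | 766.5/828.5 = 92.5% |
| 32 wk | 24 months | 56 + 730.5 = 786.5 | 728.5/786.5 = 92.6% | 724.5/786.5 = 92.1% |

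In days, 85 (147 − 62) to 131 (189 − 58) lie between the end of the window and the 3-month visit.

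Counting from first dose, where AE collection starts, gives about 60–70% to 3 months and about 93% to 24 months. Infants discharged before Day 28 reach the cut-off earlier. At the extreme of one treatment day, the shares from first dose rise to at most about 84% and 96%.

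**The case against.** The strongest reply is that the intent can be guessed. The last three periods are labelled as AEs, not treatment-emergent AEs, and there is little reason to create them if almost nothing may be tabulated in them. On that view the abbreviation TEAE is used loosely and late events will be tabulated by arm. This is plausible, but then the restricting sentence and the labels are wrong and still need editing.

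Other points have some force:

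- **Calendar time is not event share.** This stands. Protocol Appendix E places NEC among complications of the first weeks, so 58–69% is no guide to the proportion of NEC cases missed.
- **Protocol 12.4.4 makes safety analyses descriptive.** By-arm incidence could therefore satisfy the NEC and death comparison, and the AE tables would show coded NEC events by arm. This is true only for events that reach the tables.
- **Protocol 11.3 mainly governs collection,** and the SAP keeps the same collection span. The difference is one of definition. The sharper conflict is with 12.2.4.
- **The SAP takes precedence.** The clause in Protocol 12.4 covers that section. It does not plainly reach 12.2.4, does not reach 11.3, and cannot settle a conflict inside the SAP.
- **The long-term period can be partly inferred** from Protocol 12.4.7, which uses the phrase for 12- and 24-month data. A one-line definition would remove the guesswork.
- **No data are lost.** All AEs, SAEs and AEs leading to death are listed, and the DMC sees unblinded safety summaries about every 4 months. Listings still do not summarise or compare, as 12.2.4 requires.

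The efficacy ranks for NEC and death do not fill the gap. They serve tests that use one twin of a pair, while the Safety Analysis Set includes both.

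**Conclusion.** The concern holds. SAP 2.3.2.1 contradicts itself, 2.3.2.2 carries the contradiction into the SAE and death tables, and the literal rule falls short of Protocol 12.2.4. With full 28-day dosing, 58–69% of the time from birth to the 3-month corrected-age visit, and 92–93% of the time to 24 months, lies outside the window for new events. These shares rest on the date conventions stated above and measure time, not events.

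The loss would be in between-arm tabulation, not data capture. This should be corrected before unblinding. It concerns only the AE, SAE and death tables of SAP 2.3.2. It does not extend to the efficacy ranking of NEC and death, or to SAP 2.4, whose text is not in the supplied document.

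**What to change.** - **SAP 2.3.2.1:** use the treatment-emergent label only for the first period. Tabulate all AEs by onset period and arm in the 3-, 12- and 24-month periods. Delete the sentence restricting summary tables, or limit it to the first period.
- **SAP 2.3.2.2:** map the on-study and long-term follow-up periods to the four periods. Tabulate all SAEs and all AEs leading to death in each.
- **Deaths and NEC:** add a cumulative by-arm table of all deaths and all NEC cases in the Safety Analysis Set, from first dose to data cut-off, to deliver the Protocol 12.2.4 comparison. A difference from placebo with a 95% confidence interval is one suitable form.
- **SAP section 4:** state how the SAP's treatment-emergent definition differs from Protocol 11.3, covering both the end date and the dropped frequency criterion.

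The cost is SAP wording and a few extra tables from data already collected. No endpoint, significance level or sample size changes.
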